	for newly diagnosed glioblastoma GBM.
STUDY PHASE	I/II
INDICATION	Newly diagnosed glioblastoma
INVESTIGATIONAL PRODUCT OR PROCEDURE	Continuous infusion of Plerixafor
PRIMARY OBJECTIVE(S)	Efficacy as measured by progression free survival at 6 months
SECONDARY OBJECTIVE(S)	Safety of the continuous infusion of Plerixafor subsequent to irradiation
TREATMENT SUMMARY	200 micrograms per kilogram per day for four weeks, in second patient will increase to target dose of 400 micrograms per kilogram per day for four weeks, and continue treatment of subsequent patients at the target dose if tolerated.
SAMPLE SIZE	29 patients
STATISTICAL CONSIDERATIONS	Dose-escalation study with planned dose levels using the modified toxicity probability interval (mTPI). For efficacy, a greater than 50% PFS at 6 mos. PFS will be considered a positive signal and warrant further study.

SCHEMA

*Infusion will last for either two or four weeks with Phase I dose determined per the adjustment rules described in section 12.1; Phase II dose and duration determined in the Phase I

LIST OF ABBREVIATIONS AND DEFINITION OF TERMS

ABW Actual Body Weight ADL Activities of daily living AE Adverse event CBC Complete blood count CMAX Maximum concentration of drug CNS Central nervous system CRF Case report/Record form CR Complete response CTCAE Common Terminology Criteria for Adverse Ever DLT Dose Limiting Toxicity DSMB Data Safety Monitoring Board ECG Electrocardiogram GBM Glioblastoma GI Gastrointestinal HIV Human Immunodeficiency Virus IBW Ideal Body Weight IRB Institutional Review Board IV Intravenous KPS Karnofsky Performance Score MTPI Modified Toxicity Probability Interval OS Overall survival PLT Platelet PD Progressive disease PFS Progression free survival	ts
AE Adverse event CBC Complete blood count CMAX Maximum concentration of drug CNS Central nervous system CRF Case report/Record form CR Complete response CTCAE Common Terminology Criteria for Adverse Ever DLT Dose Limiting Toxicity DSMB Data Safety Monitoring Board ECG Electrocardiogram GBM Glioblastoma GI Gastrointestinal HIV Human Immunodeficiency Virus IBW Ideal Body Weight IRB Institutional Review Board IV Intravenous KPS Karnofsky Performance Score MTPI Modified Toxicity Probability Interval OS Overall survival PLT Platelet PD Progressive disease PFS Progression free survival	ts
CBC Complete blood count CMAX Maximum concentration of drug CNS Central nervous system CRF Case report/Record form CR Complete response CTCAE Common Terminology Criteria for Adverse Ever DLT Dose Limiting Toxicity DSMB Data Safety Monitoring Board ECG Electrocardiogram GBM Glioblastoma GI Gastrointestinal HIV Human Immunodeficiency Virus IBW Ideal Body Weight IRB Institutional Review Board IV Intravenous KPS Karnofsky Performance Score MTPI Modified Toxicity Probability Interval OS Overall survival PLT Platelet PD Progressive disease PFS Progression free survival	ts
CMAX CNS Central nervous system CRF Case report/Record form CR Complete response CTCAE Common Terminology Criteria for Adverse Ever DLT Dose Limiting Toxicity DSMB Data Safety Monitoring Board ECG Electrocardiogram GI Gastrointestinal HIV Human Immunodeficiency Virus IBW Ideal Body Weight IRB Institutional Review Board IV Intravenous KPS Karnofsky Performance Score MTPI Modified Toxicity Probability Interval OS Overall survival PLT Platelet PD Progressive disease PFS Progression free survival	ts
CNS CRF Case report/Record form CR Complete response CTCAE DLT Dose Limiting Toxicity DSMB Data Safety Monitoring Board ECG Electrocardiogram Glioblastoma GI GI Gastrointestinal HIV Human Immunodeficiency Virus IBW Ideal Body Weight IRB Institutional Review Board IV Intravenous KPS Karnofsky Performance Score MTPI Modified Toxicity Probability Interval OS Overall survival PLT Platelet PD Progressive disease PFS Progression free survival	ts
CRF Complete response CTCAE Common Terminology Criteria for Adverse Ever DLT Dose Limiting Toxicity DSMB Data Safety Monitoring Board ECG Electrocardiogram GBM Glioblastoma GI Gastrointestinal HIV Human Immunodeficiency Virus IBW Ideal Body Weight IRB Institutional Review Board IV Intravenous KPS Karnofsky Performance Score MTPI Modified Toxicity Probability Interval OS Overall survival PLT Platelet PD Progressive disease PFS Progression free survival	ts
CR Complete response CTCAE Common Terminology Criteria for Adverse Ever DLT Dose Limiting Toxicity DSMB Data Safety Monitoring Board ECG Electrocardiogram GBM Glioblastoma GI Gastrointestinal HIV Human Immunodeficiency Virus IBW Ideal Body Weight IRB Institutional Review Board IV Intravenous KPS Karnofsky Performance Score MTPI Modified Toxicity Probability Interval OS Overall survival PLT Platelet PD Progressive disease PFS Progression free survival	ts
CTCAE Dust Limiting Toxicity Dose Limiting Toxicity Data Safety Monitoring Board ECG Electrocardiogram GI GI Gastrointestinal HIV Human Immunodeficiency Virus IBW Ideal Body Weight IRB Institutional Review Board IV Intravenous KPS Karnofsky Performance Score MTPI Modified Toxicity Probability Interval OS Overall survival PLT Platelet PD Progressive disease PFS Progression free survival	ts
DLT Dose Limiting Toxicity DSMB Data Safety Monitoring Board ECG Electrocardiogram GBM Glioblastoma GI Gastrointestinal HIV Human Immunodeficiency Virus IBW Ideal Body Weight IRB Institutional Review Board IV Intravenous KPS Karnofsky Performance Score MTPI Modified Toxicity Probability Interval OS Overall survival PLT Platelet PD Progressive disease PFS Progression free survival	
DSMB ECG Electrocardiogram GBM Glioblastoma GI HIV Human Immunodeficiency Virus IBW Ideal Body Weight IRB Institutional Review Board IV Intravenous KPS Karnofsky Performance Score MTPI Modified Toxicity Probability Interval OS Overall survival PLT Platelet PD Progressive disease PFS Progression free survival	
ECG Electrocardiogram GBM Glioblastoma GI Gastrointestinal HIV Human Immunodeficiency Virus IBW Ideal Body Weight IRB Institutional Review Board IV Intravenous KPS Karnofsky Performance Score MTPI Modified Toxicity Probability Interval OS Overall survival PLT Platelet PD Progressive disease PFS Progression free survival	
GBM Glioblastoma GI Gastrointestinal HIV Human Immunodeficiency Virus IBW Ideal Body Weight IRB Institutional Review Board IV Intravenous KPS Karnofsky Performance Score MTPI Modified Toxicity Probability Interval OS Overall survival PLT Platelet PD Progressive disease PFS Progression free survival	
GI Gastrointestinal HIV Human Immunodeficiency Virus IBW Ideal Body Weight IRB Institutional Review Board IV Intravenous KPS Karnofsky Performance Score MTPI Modified Toxicity Probability Interval OS Overall survival PLT Platelet PD Progressive disease PFS Progression free survival	
HIV Human Immunodeficiency Virus IBW Ideal Body Weight IRB Institutional Review Board IV Intravenous KPS Karnofsky Performance Score MTPI Modified Toxicity Probability Interval OS Overall survival PLT Platelet PD Progressive disease PFS Progression free survival	
IBWIdeal Body WeightIRBInstitutional Review BoardIVIntravenousKPSKarnofsky Performance ScoreMTPIModified Toxicity Probability IntervalOSOverall survivalPLTPlateletPDProgressive diseasePFSProgression free survival	
IRBInstitutional Review BoardIVIntravenousKPSKarnofsky Performance ScoreMTPIModified Toxicity Probability IntervalOSOverall survivalPLTPlateletPDProgressive diseasePFSProgression free survival	
IVIntravenousKPSKarnofsky Performance ScoreMTPIModified Toxicity Probability IntervalOSOverall survivalPLTPlateletPDProgressive diseasePFSProgression free survival	
MTPI Modified Toxicity Probability Interval OS Overall survival PLT Platelet PD Progressive disease PFS Progression free survival	
MTPI Modified Toxicity Probability Interval OS Overall survival PLT Platelet PD Progressive disease PFS Progression free survival	
OS Overall survival PLT Platelet PD Progressive disease PFS Progression free survival	
PD Progressive disease PFS Progression free survival	
PFS Progression free survival	
PFS Progression free survival	
DD 2.1	
PR Partial response	
RANO Revised Assessment in Neuro-oncology	
RR Response rate	
SAE Serious adverse event	
SD Stable disease	
SOC Standard of care	
SLD Sum of the longest diameter	
SPD Sum of the products of the diameter	
TMZ Temozolomide	
TTP Time to progression	
ULN Upper limit of normal	
UNK Unknown	
WBC White blood cell	
XRT Chemoradiation	

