2.4 Study Design

For clinicaltrials.gov and Stanford Clinical Trials Directory compliance

- State the primary purpose for the protocol:
 - o Treatment
- State the interventional model from these choices:
 - Single Group
- State the number of intervention arms.
 - o One
- State whether the study will be masked (at least one party is unaware of the treatment)
 - o **Open**: no masking is used
- State whether the study is randomized.
 - o No
- State type of primary outcome or outcome that the protocol is designed to evaluate:

Safety (Phase I) Efficacy (Phase II)

Phase I

The Phase I is designed to evaluate safety. A total of 9 newly diagnosed patients will be enrolled within four weeks of surgery (biopsy, partial resection or gross total resection). In order to minimize the chances for local angiogenic migration into the irradiated field, irradiation will be administered to the area encompassed by T2 FLAIR imaging plus a 2 cm margin to 46 Gy with a focal boost to the enhancing area to 60 Gy over a six-week period. Temozolomide 75 mg/M²/d starting the day of radiotherapy will be administered for 42 days concurrent with irradiation. Eight days prior to irradiation completion, patients will have a PICC line placed. Seven days prior to irradiation completion, the continuous infusion of Plerixafor will be initiated using a step-wise dose escalation based on the modified toxicity probability interval (mTPI) method. All treatments will start one week prior to completion of radiotherapy with concurrent temozolomide for patients with newly diagnosed glioblastoma. This dose escalation study begins with an intermediate dose of 200 µg/kg per day for four weeks. The first 3 patients will be enrolled at this starting dose. Enrollment within a dose level will be staggered so that there is at least 1 week between patients. If tolerability and safety is established after the 4 week treatment period, then the fourth patient will be enrolled at the higher target dose of 400 µg/kg per day for four weeks. We will wait one week after the last infusion at one dose level before proceeding to the next dosage level.

If a patient experiences a DLT, then s/he will be removed from study and the next patient treated at the lower dose level as dictated by the mTPI table.

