10.1.1 Relevant Subset

The first 9 patients will be treated accordingly to the dosing algorithm depicted in Table 12.1. The starting dose will be 200 micrograms per kilogram per day for four weeks. We will wait one week after the completion of the infusion at one dose level before proceeding. Once the final dose is determined at the Phase I portion of this study, then another 20 patients will be treated at the dose determined maximally tolerable.

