The prior is a beta with parameters 1 and 1 (roughly equivalent to two observations, one of these a DLT). Briefly, with the above settings, when the posterior probability falls below 0.25 (0.30-0.05), escalation to the next higher dose level is indicated; when the posterior probability falls above 0.35 (0.30+0.05), de-escalation is recommended; otherwise the next patient is to be treated at the same dose level. The rules for escalation and de-escalation for this design are contained in Table 12.1; they do not need to be modified during the course of the study. At the end of the study the toxicity data at all doses is combined using the "pool adjacent violators" algorithm to make toxicity probabilities non-decreasing; the maximum tolerated dose is calculated as the dose level that comes closest to the target toxicity level.

Table 12.1 show the action to be taken as each patient becomes evaluable for toxicity. It is used for all dose levels as follows:

- E means that the next patient is to be treated at the next higher dose. If the current dose is the highest planned $400 \mu g/kg/d \times 28 d$, the next patient is to be treated at the **same** dose level.
- S means that the next patient is to be treated at the same dose level. Note that a minimum of 3 subjects must be studied at a dose before escalation is indicated.
- D means that the next patient is to be treated at the next lower dose. If the current dose is the

- lowest planned 200 µg/kg/d x 14 d, the next patient is to be treated at the same dose level.
- U means that the current dose level is too toxic. No further patients are to be treated at this or at any higher dose level. If the current dose level is the lowest planned (200 μ g/kg/d x 2 wks total dose) no further patients will be treated. If the current dose level is not the lowest planned, the next patient should be studied at the next lowest dose (100 μ g/kg/d x 4 wks).

These definitions are in accord with our reading of the code used to produce the simulations which validated the mTPI design.

Toxicity will be monitored in the expansion phase at each increment of 5 patients. If DLT is observed in one out of the first 5 patients, or 2 of the first 10, or 2 of the first 15, toxicity will be reviewed to assess whether the trial should continue. This stopping rule has a 5% chance of being triggered if the true DLT toxicity rate is 5%, it has a 62% chance of being triggered if the true DLT rate is 30%.

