12.4.1 Analysis Population

A total of 9 patients will be treated in the Phase I component with the first at the starting dose of 200 $\mu g/kg/d \times 4$ wks. If the regimen proves too toxic or if none of the dose levels appears to reach 30% DLT, fewer patients may be treated.

Table 12.1

		Cumulative Number of Patients Treated at This Dose								
		1	2	3	4	5	6	7	8	9
	0	E	E	Е	Е	Е	Е	E	Е	Ε
_	1	D	S	S	S	S	Е	E	Е	Е
.	2		U	D	S	S	S	S	S	S
umber Dose	3			U	U	D	S	S	S	S
E O	4				U	U	U	D	D	S
z "	5					U	U	U	U	U
를 Œ	6						U	U	U	U
mulat Ts at	7							U	U	U
Ē º	8								U	U
ರ ದ	9									U

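### The documents conflict on when Phase I moves from 200 to 400 µg/kg/day: the synopsis escalates at the second patient, section 2.4 and the Table 12.1 key require three patients first, and the table itself does not show that minimum.

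*Combined protocol and SAP*

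**What the plan says.** The statements below all bear on escalation from the starting dose (200 µg/kg/day for four weeks) to the target dose (400 µg/kg/day for four weeks).

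- **Synopsis, Treatment Summary.** After the starting dose, the plan is that dosing "in second patient will increase to target dose of 400 micrograms per kilogram per day for four weeks". The tolerability condition in that sentence is attached to the patients who follow. No condition is stated for the second patient. The footnote to the schema refers readers elsewhere: "Phase I dose determined per the adjustment rules described in section 12.1".
- **Section 2.4, Phase I.** "The first 3 patients will be enrolled at this starting dose". If safety is established, "then the fourth patient will be enrolled at the higher target dose of" 400 µg/kg/day.
- **Section 12.1, key to Table 12.1.** The entry for E reads: "E means that the next patient is to be treated at the next higher dose". Its only stated exception is the highest dose. The entry for S, which keeps the next patient at the same dose, carries a further sentence: "Note that a minimum of 3 subjects must be studied at a dose before escalation is indicated". The table is to be consulted each time a patient becomes evaluable, and at every dose level.
- **Table 12.1 (printed under 12.4.1).** The row for zero DLTs shows E in all nine columns, including those for one and two patients. No cell carries a mark or footnote.
- **Section 10.1.1.** "The first 9 patients will be treated accordingly to the dosing algorithm depicted in Table 12.1".
- **Section 12.4.1.** "A total of 9 patients will be treated in the Phase I component with the first at the starting dose of 200" µg/kg/day for four weeks.

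**The concern.** Escalation is the main safety decision in Phase I, and this step doubles the daily dose. If the first patient has no DLT, the protocol gives two answers to the question of what the second patient receives. It is 400 according to the synopsis and the unrestricted table cell, and 200 according to section 2.4 and the note in the key.

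The choice determines how much evidence stands behind the doubled dose. It also determines how the nine Phase I patients divide between dose levels, and so the data that go into the final estimate of the maximum tolerated dose. Because the table serves every dose level, the same uncertainty applies to any re-escalation after a step down. Section 2.4 gives no help there, since it speaks only of the starting dose. The note under S is then the only statement of a minimum.

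**Working it through.** **1. Are the E entries for one and two patients genuine?** The inputs come from section 12.1: target DLT rate 0.30, margin ±0.05, prior Beta(1,1). The modified toxicity probability interval (mTPI) rule compares the posterior probability in each interval divided by the interval's width, and the largest value decides. With 0 DLTs in n patients the posterior is Beta(1, n+1), so P(rate ≤ c) = 1 − (1 − c)^(n+1).

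For n = 1:
- E: (1 − 0.75²)/0.25 = 0.4375/0.25 = 1.75
- S: (0.75² − 0.65²)/0.10 = (0.5625 − 0.4225)/0.10 = 1.40
- D: 0.65²/0.65 = 0.65

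| DLTs/patients | E | S | D | Result | Printed |
|---|---|---|---|---|---|
| 0/1 | 1.75 | 1.40 | 0.65 | E | E |
| 0/2 | 2.31 | 1.47 | 0.42 | E | E |
| 0/3 | 2.73 | 1.38 | 0.27 | E | E |

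All 54 cells of Table 12.1 reproduce in this way if D becomes U when P(rate > 0.30) exceeds 0.95. That cut-off is an assumption, as the documents do not give it. Lowering it to 0.90 or 0.92 changes only some D cells to U and leaves the zero-DLT row unchanged. The E entries are therefore real output of the method and not a reading error. The three-subject minimum is an added restriction that has not been carried into the table.

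**2. The rules side by side, if no DLT occurs** (dose in µg/kg/day)

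| Source | Patient 2 | Patient 3 | Patient 4 |
|---|---|---|---|
| Synopsis | 400 | 400 if tolerated | 400 if tolerated |
| Table cells with the E entry alone | 400 | 400 | 400 |
| Section 2.4 | 200 | 200 | 400 |
| Table with the note under S applied to E | 200 | 200 | 400 |

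**3. Chance of no DLT by the first escalation decision.** With true DLT rate p at the starting dose and independent patients, this is (1 − p) after one patient and (1 − p)³ after three. At p = 0.30 it is 0.70 and 0.70³ = 0.343. At p = 0.40 it is 0.60 and 0.60³ = 0.216.

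| True DLT rate | After 1 patient | After 3 patients |
|---|---|---|
| 10% | 90.0% | 72.9% |
| 20% | 80.0% | 51.2% |
| 30% (target) | 70.0% | 34.3% |
| 40% | 60.0% | 21.6% |
| 50% | 50.0% | 12.5% |

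**4. What the data would exclude at that moment.** The one-sided 95% upper limit on the DLT rate after 0/n is 1 − 0.05^(1/n). For n = 1 it is 95%, and for n = 3 it is 1 − 0.05^(1/3) = 63%.

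**5. Division of the nine patients.** If no DLT occurs at either level and all nine are treated, the split between 200 and 400 is 1 + 8 under one rule and 3 + 6 under the other.

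**The case against.** The strongest reply is that the detailed text already settles on three. Table 12.1 cannot be used without its key, and the key contains a general, mandatory minimum of three before escalation. On that reading the E cells for one and two patients are raw mTPI output and the note says when they may be acted on. Section 2.4 agrees, and the schema footnote defers to 12.1. That leaves one line of the synopsis against two detailed passages.

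Much of this stands. A reader might infer that anyone following the table must escalate after one patient. The documents do not support that, because the table's own key carries the minimum. Three further inferences also fail:

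- Section 12.4.1 does not say that only one patient receives the starting dose. It says where dosing begins, which fits either rule.
- Section 12.1 says the table's rules need no modification while the trial runs. That concerns recalculation as data accrue and does not give the table precedence over the note.
- The synopsis does not say that one DLT-free patient is sufficient. It states no DLT condition for the second patient. The zero-DLT condition comes from the table cell.

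The reply does not remove the conflict. The synopsis names the second patient outright, and no reading of the note changes that. The note is printed under S, while the E entry lists a different exception and says nothing about a minimum. The table is unmarked. The footnote's reference to 12.1 is not a statement that 12.1 overrides the treatment summary printed above it.

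**Conclusion.** The contradiction is real and concerns a patient-safety decision. The synopsis conflicts openly with section 2.4 and with the note in the key. Table 12.1 is ambiguous, because its cells and the E entry omit a minimum that the key states under another letter. The balance of the detailed text favours three, but no passage says which text prevails.

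At a true DLT rate equal to the 30% target, the chance that no DLT has been seen by the first escalation decision is 70% after one patient and 34% after three. At 40% it is 60% and 22%. These figures assume independent patients with a common DLT rate. Apart from the 30% target, the rates are illustrative.

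A reader might take them as the overall chance of escalating, which they are not. They compare decisions taken at different times, and Table 12.1 also allows escalation later, for example at one DLT in six patients. The 1 + 8 and 3 + 6 splits hold only if no DLT occurs, and section 12.4.1 allows fewer than nine patients in some circumstances.

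**What to change.** Reconcile the synopsis, section 2.4, the key in section 12.1 and Table 12.1 to a single minimum number of evaluable patients at a dose before escalation. State that minimum in the definition of E instead of under S. Mark it in the zero-DLT cells for one and two patients, so that table, key and text give the same instruction at every dose level. Section 12.4.1 needs at most a clarifying word.

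Which minimum applies is for the sponsor to decide, and the passages that disagree with the decision should be amended to match it. The cost is a wording amendment and a mark on two table cells. The Phase I maximum stays at nine, so no patients are added.

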1. OBJECTIVES

1.1. Primary Objectives

- To assess the safety of using continuous infusion Plerixafor beginning one week prior to the end of concurrent chemotherapy with Temozolomide and radiation therapy in patients with newly diagnosed GBM.
- To assess the efficacy of Plerixafor as measured by progression free survival at 6 months (PFS6) from the start of irradiation.

2. BACKGROUND

2.1 Glioblastoma

Although radiotherapy delays the recurrence of most glioblastomas (GBMs), these tumors invariably regrow and prove fatal for more than 75% of the patients by two years after diagnosis. Importantly, most recurrent tumors recur within the field of high dose radiation [1-4]. Thus, any method of reducing local recurrences will improve the survival of GBM patients. Following irradiation, tumor recurrence requires the formation of new blood vessels. Inhibiting blood vessel growth will delay or prevent regrowth of GBM within an irradiated field and thus improve patient outcome.

Though it is often unrecognized by investigators in the field, tumors have two main ways to grow blood vessels: By angiogenesis, the sprouting of endothelial cells from nearby blood vessels, and vasculogenesis, the formation of blood vessels by circulating cells, primarily of bone marrow origin. The presence of circulating proangiogenic cells was first demonstrated by Asahara and colleagues [5], and is now recognized as a way in which blood vessels can be formed in damaged normal tissues and tumors, particularly following therapy [6, 7]. We have shown that local tumor irradiation, by killing the endothelial cells in and surrounding the tumor, abrogates local angiogenesis [8, 9]. The tumor must therefore rely on the vasculogenesis pathway for regrowth after irradiation.

